4. SELECTION OF STUDY POPULATION

Number of patients: 86 adult patients with established insulin-requiring T1D and evidence of IR will be enrolled, provided that they fully meet all of the Inclusion Criteria and none of the Exclusion Criteria described in Sections 4.1. and 4.2. below.

4.1. INCLUSION CRITERIA

To be eligible for inclusion into this study, each patient must fulfil the following inclusion criteria:

1. clinical diagnosis of autoimmune T1D as documented by positive T1D-related autoantibodies [the presence of at least one or more of: Insulin autoantibodies (**IAA**), Anti-GAD (**GAD65**), Anti-IA2 (**IA2**), Zinc Transporter 8 (**ZnT8**) must be documented from medical records or new laboratory measurement (not including IAA)];
2. age 21-65 years at the time of consent;
3. T1D duration > 1 year;
4. detectable fasting C-peptide as per the result of screening laboratory measurement;
5. current insulin standard of care (**ISOC**), either established use of an insulin pump (closed loop system excluded) or a stable dose level and dose frequency for the last two months prior to screening, with no plans to switch the modality of insulin administration during the trial;
6. routine use of a self-owned (if applicable) CGM system that can record glucose concentrations continuously for at least 7 days;
7. HbA1c $\geq 7.5\%$ as per the result of screening laboratory measurement;
8. evidence of IR based on a total daily insulin dose >0.8 U/kg/day;
9. subject is overweight or obese with a BMI of between 24-33 kg/m², inclusive;
10. ability to comply with all protocol procedures for the duration of the study, including scheduled follow-up visits and examinations, and willing to be contacted by clinical trial staff;
11. provision of written informed consent prior of any study-related procedure not part of standard medical care.

4.2. EXCLUSION CRITERIA

Patients who meet any of the following criteria are NOT eligible for inclusion in the study:

1. use of a “closed loop system” for integrated glucose reading/insulin infusion;
2. known or suspected hypersensitivity to non-steroidal anti-inflammatory drugs or any excipient of the investigational medicinal products (e.g. lactose and croscarmellose) as well as patients with congenital lactase deficiency, galactosaemia or glucose-galactose intolerance will have to be excluded;
3. use of non-insulin medications for adjunctive blood glucose control (e.g: antidiabetic agents such as metformin, sulfonylureas, glinides, thiazolidinediones, exenatide, liraglutide, DPP-IV inhibitors, SGLT-2 inhibitors or amylin) within one month of randomization as well as required in the participant’s standard of care;
4. use of medications for weight reduction, such as: Belviq (lorcaserin), Qsymia (Phentermine + topiramate), Orlistat (xenical) within one month of randomization as well as required in the participant’s standard of care;
5. use of a medication such as stimulants, antidepressants and/or psychotropic agents that could affect weight gain or glycemic control of T1D;
6. treatment with drugs metabolized by CYP2C9 with a narrow therapeutic index [i.e., phenytoin, warfarin, and high dose of amitriptyline (>50 mg/day)];
7. use of angiotensin-converting enzyme inhibitors, interferons, quinidine antimalarial drugs, lithium, niacin;
8. evidence of QTcF >470 msec and a history of significant cardiovascular disease/abnormality;
9. any condition, including unstable diet and disordered eating behaviour, that in the judgment of the investigator will adversely affect patient’s safety or the completion of the protocol or otherwise confound study outcome;
10. pregnancy: a) positive or missing pregnancy test (quantitative beta hCG) at screening; b) women of child-bearing potential and fertile men who do not agree to use effective contraceptive measures up

to 2 months following trial discharge [effective contraceptive measures include a hormonal birth control (e.g. oral pills, long term injections, vaginal ring, patch); the intrauterine device (IUD); a double barrier method (e.g. condom or diaphragm plus spermicide foam)]; lactating women;

11. clinical diagnosis of celiac disease that is in poor control as defined by most recent tissue transglutaminase (tTG) that is in the abnormal range;
12. history of ≥ 1 Diabetic Ketoacidosis (**DKA**) event in the past 6 months;
13. hypoalbuminemia defined as serum albumin < 3 g/dL;
14. hepatic dysfunction defined by increased ALT/AST > 3 x upper limit of normal (**ULN**) **and** increased total bilirubin > 3 mg/dL [> 51.3 μ mol/L];
15. moderate to severe renal impairment calculated by estimated Glomerular Filtration Rate (**eGFR**) < 60 mL/min/1.73 m² as determined using Chronic Kidney Disease Epidemiology Collaboration (**CKD-EPI**) creatinine equation;
16. past (within 1 month prior to screening) or current administration of any immunosuppressive medications (including oral or systemically injected steroids) and use of any investigational agents, including any agents that impact the immune response;
17. a condition already known which interferes with the ability to accurately determine glycated HbA1c. Examples include: genetic variants (e.g. HbS trait, HbC trait), elevated fetal hemoglobin (HbF) and chemically modified derivatives of hemoglobin (e.g. carbamylated Hb in patients with renal failure); any condition that shortens erythrocyte survival or decreases mean erythrocyte age (e.g., recovery from acute blood loss, hemolytic anemia); iron deficiency anemia, iron replacement therapy;
18. significant systemic infection during the 4 weeks before the first dose of study drug (e.g., infection requiring hospitalization, major surgery, or i.v. antibiotics to resolve; other infections, e.g., bronchitis, sinusitis, localized cellulitis, candidiasis, or urinary tract infections, must be assessed on a case-by-case basis by the investigator regarding whether they are serious enough to warrant exclusion).

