5.3.2. Criteria for discontinuation of the IMP

The IMP will be discontinued in the case:

- QTcF is either > 500 msec or increases by > 60 msec from screening measurement on two consecutive ECG readings taken 1 hour apart;
- The patient develops any significant cardiovascular disease/abnormality;
- The patient develops renal (calculated eGFR < 60 mL/min) or hepatic (increased ALT/AST > 3 x ULN and increased total bilirubin > 3mg/dL [$>51.3 \mu\text{mol/L}$]) dysfunction as well as hypoalbuminemia (serum albumin <3 g/dL);

- Pregnancy occurs (subjects of child-bearing potential);
- The patient develops Diabetic Ketoacidosis (**DKA**) or hypoglycemic coma.

Occurrence of any condition that qualify the patient to treatment discontinuation will be specifically monitored through ECG readings and safety laboratory tests obtained at week 4 (visit 2b) and 11/12 (visit 3) during treatment. Pregnancy (urine dipstick) will be also tested at week 11/12 (visit 3).

In addition, the IMP will be immediately discontinued in the event of any other possibly drug related occurrences that the study physician believes might compromise patient's safety.

If the IMP administration is prematurely discontinued, the primary reason for discontinuation must be recorded in the eCRF. Patients who discontinue the treatment with the IMP will NOT be withdrawn from the study by default but will be asked to complete safety and efficacy observations as per the protocol, unless otherwise they withdraw their consent.

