6.1.2. Visit schedule and events/procedures

All subjects will follow the study procedures outlined below (see also grid in [Section 2](#) above).

Every effort should be made to adhere to the visit schedule. Visits should be scheduled at the designated time-point. If unavoidable, an unscheduled visit may be performed, but the schedule for subsequent visits must be maintained so that the total duration of the study period per patient is as close as possible to 30 weeks. If a visit is scheduled at a time other than the protocol designated time, careful consideration must be given to the amount of study medication the subject has available.

Patients should be counseled to fast (no food or drink except water and non-study medications as prescribed) for at least 8 hours prior to all study visits where blood will be collected.

Each patient will be involved in the study for a screening visit, a randomization visit, the treatment period of 26 weeks (14 days on /14 days off) with 3 follow-up visits to the clinical research site scheduled up to week 28 after the 1st IMP dose.

Visit schedule and events/procedures are detailed in the sections below. Visits 2b and 3 are scheduled during the 14 days off treatment, while visit 4 is set in the 2 weeks after treatment completion (last IMP dose in cycle 7).

CCI

Visit 1: Screening: The study physician or designee will present to/discuss with the study subject the clinical trial and answer all questions. If the patient is able and willing to participate, after the informed consent has been obtained, study staff will:

- assess past medical history to confirm T1D (e.g. results of past auto-antibody testing),
- determine daily insulin requirement (U/kg/day - expressed as the average of the last 3 days) and its stability,
- measure body weight, height, waist and waist/hip circumference,
- calculate [REDACTED] BMI,
- record the use of concomitant medication,
- establishing the presence of IR as described (inclusion criteria, bullet 8)¹⁻³.

Screening evaluation also include blood sampling for the assessment of:

- HbA1c,
- fasting C-peptide,
- standard safety laboratory tests,

- pregnancy in subjects with reproductive potential; post-menopausal women, defined as no menses for 12 months without an alternative medical cause, will not undergo pregnancy testing.
- T1D auto-antibody (excluding IAA) should past data not be available.

Vital signs (blood pressure and heart rate) will be measured and an ECG performed.

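### Exclusion 8 joins QTcF >470 msec and cardiovascular history by 'and' where 'or' is probably meant; read literally, neither alone keeps a patient out

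*Protocol*

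**What the plan says.** **Entry.** Section 4.2 makes any single numbered item sufficient to exclude. Item 8, repeated in the synopsis, is "evidence of QTcF >470 msec and a history of significant cardiovascular disease/abnormality".

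**Stopping.** Section 5.3.2 gives two separate bullets. One applies when "QTcF is either > 500 msec or increases by > 60 msec from screening measurement", confirmed "on two consecutive ECG readings taken 1 hour apart". The other reads "The patient develops any significant cardiovascular disease/abnormality".

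**Other uses of *and*.** In section 4.2, exclusion 14 (hepatic dysfunction) sets in bold the *and* between raised transaminases and raised bilirubin. Exclusion 16 uses a plain *and* to add a further alternative to immunosuppressive drugs: "and use of any investigational agents, including any agents that impact the immune response".

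**ECG schedule.** ECGs are planned at screening and at visits 2b, 3 and 4, with none at visit 2, when the first dose is taken on site. Section 5.3.2 says the conditions for stopping "will be specifically monitored through ECG readings and safety laboratory tests obtained at week 4 (visit 2b) and 11/12 (visit 3) during treatment". Section 6.1.2 says: "Visits 2b and 3 are scheduled during the 14 days off treatment, while visit 4 is set in the 2 weeks after treatment completion".

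**The concern.** An eligibility rule is applied as written, by many people, at sites in two countries. As printed, item 8 needs both a long QTcF and a cardiovascular history, so it screens out only the patients who have both. Section 2.5.3 names QT prolongation as the potential human safety concern arising from the animal work, so this is the item that should be unambiguous.

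The gap does not close quickly after entry. There is no ECG at visit 2, so a patient admitted with a long QTcF would next have a scheduled ECG at visit 2b, after the whole of cycle 1. The cardiovascular stopping bullet speaks of disease that develops, so it does not plainly reach disease already present at entry.

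Only patient safety is at stake. ECG is not among the safety endpoints in section 7.2, and the primary endpoint, its analysis and the listed safety endpoints do not depend on item 8.

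**Working it through.** **1. Item 8 under the two readings**

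| Screening QTcF | Cardiovascular history | Excluded under *and* | Excluded under *or* |
|---|---|---|---|
| ≤470 msec | no | no | no |
| >470 msec | no | **no** | yes |
| ≤470 msec | yes | **no** | yes |
| >470 msec | yes | yes | yes |

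The readings differ in the two middle rows. The second row has no upper bound, so it includes values above 500 msec. Such a patient is beyond the numerical threshold of section 5.3.2 at entry, although the stopping rule itself also needs a second reading an hour later.

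**2. Which reading the protocol supports**

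- Section 5.3.2 lists the same two conditions as separate bullets, each sufficient to stop. An entry rule that requires both would be looser than the stopping rule that follows it.
- Exclusion 14 in section 4.2 stresses its *and* where both parts are required. Item 8 has no such emphasis.
- Exclusion 16 shows the authors using a plain *and* to list alternatives.

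All three point to *or*. None of them changes what item 8 says.

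**3. Secondary observation: ECG days against dosing days**

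Inputs: 7 cycles of 14 days on and 14 days off (section 5.2); latest evening dose 23:30 (section 5.2); human half-life 11–19 h and peak at 1–3 h (section 2.4); dog QT effect at 2–4 h after dosing (section 2.3). Assumptions: visits at 07:30, single-compartment decay, parent drug only.

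- Plan's own figure: cycle k runs from day 28(k−1)+1 to day 28(k−1)+14. The last dosing day is 28×6+14 = 182, and 182/7 = 26 weeks, as stated.
- Dosing days: 7×14 = 98 of 182 (54%).
- Visit 2b (week 4, days 22–28), visit 3 (days 71–84) and visit 4 (days 183–196) contain 0, 0 and 0 dosing days. Counting 28 elapsed days for week 4 would give day 29, the start of cycle 2, but section 6.1.2 places the visit in the off period.
- Fraction of parent drug left after t hours = 0.5^(t/half-life).
- Earliest visit 2b: day 14 at 23:30 to day 22 at 07:30 = 176 h. 0.5^(176/19) = 0.16%; 0.5^(176/11) = 0.0015%.
- Visits 3 and 4, for half-lives of 11 and 19 h: first morning (8 h) 60% and 75%; second (32 h) 13% and 31%; third (56 h) 3% and 13%; eighth (176 h) 0.16% or less.

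Visit 2b therefore sees essentially no parent drug. Visits 3 and 4 see a meaningful amount only in the first days of their windows. Visit 4 follows the last dose and cannot trigger stopping.

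**The case against.** **On item 8.** The best reply is that nobody would misread it. Exclusion 16 shows *and* used as a list joiner, section 5.3.2 shows what was meant, and exclusion 9 lets the investigator refuse anyone whose condition would adversely affect safety. This stands as an argument about likely conduct: the intended rule can be inferred, and most investigators would probably apply it. It does not defend the text. It concedes that *or* is meant, and exclusion 9 depends on individual judgment.

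**On the ECGs.** Here the reply is stronger, and most of it stands.

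- The off-period placement is stated openly in section 6.1.2, next to redacted text that may explain it. The schedule grid labels weeks 1 to 26 as the treatment phase, so calling these checks monitoring during treatment is not a contradiction.
- Phase I tested up to 400 mg b.i.d. Core-laboratory review of QTcF changes and of the PK–PD relationship found no clinically significant effect on repolarization (section 2.5.3).
- Fifty T1D patients took this dose for 3 cycles, and none of the serious events listed for them is cardiac. That is not QTcF evidence, but section 2.6.2.1 reports no safety concern in that trial.
- Other safeguards exist: unscheduled visits, calls at least every 30–45 days, stopping on the study physician's judgment, and DMC safety review at least every 4 months. Most depend on symptoms or reported events, so they do not replace an on-drug ECG, but they lower the stakes.
- With 12-hourly dosing, the level just before a dose is 0.5^(12/11) = 47% to 0.5^(12/19) = 65% of that just after the previous one. An ECG on the first off morning (60–75% left) therefore sees at least a dosing-day trough.

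What remains open is limited. No ECG results or timing for the T1D trial appear in the protocol, which refers readers to the Investigator's Brochure for detail. This trial gives 98 dosing days against 3×14 = 42 in that trial.

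**Conclusion.** Item 8 is wrong as written and should be corrected in both places. Its size can be stated only as a class of patients: anyone with exactly one of the two conditions, including QTcF above 500 msec without cardiovascular history. No head count is possible, because the protocol gives no screening QTcF distribution or prevalence of cardiovascular history. The conclusion rests on the literal reading; that *or* was intended is an inference from sections 4.2 and 5.3.2, though a strong one.

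A reader might infer three stronger things that the document does not support.

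- *The sponsor meant to admit patients above 500 msec.* The separate stopping bullets point the other way.
- *The QTcF stopping rule cannot work, so the visit schedule must change.* Persistent or delayed effects could still be seen off drug, and early visit 3 dates carry substantial exposure. The supportable statement is that the scheduled checks, visit 2b above all, are unlikely to detect an acute exposure-driven effect. That is a debatable trade-off.
- *Ladarixin prolongs QT in patients.* The signal is in dogs, in the 9-month study at 60 mg/kg/day and above. Its margin to human exposure cannot be judged from the protocol, and the Phase I review is reassuring.

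The residual-exposure figures assume single-compartment decay of the parent drug. Human metabolite half-lives are not given.

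**What to change.** **Required.** In exclusion 8 of the synopsis and of section 4.2, replace the *and* between the two conditions by *or*, so that QTcF >470 msec or the cardiovascular history each excludes alone. The cost is one word in two places in one amendment. No visit, endpoint, analysis or sample size changes. Some patients whom a literal reading would admit become ineligible, which is the evident purpose of the item.

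**Optional, for the sponsor to weigh.** Consider one ECG on a dosing day near steady state, which section 2.4 puts at about day 5–6, at roughly 1–3 h after a dose. One way is to move visit 2b, which holds only an ECG and safety laboratory tests, to days 8–14 of cycle 1, drawing blood before an on-site dose and taking the ECG afterwards. This has real costs:

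- Cycle 1 laboratory tests would be drawn on drug, and the post-cycle tests would be lost.
- Patients already fast "for at least 8 hours prior to all study visits where blood will be collected". Section 5.2 separates doses from breakfast and dinner by 2 hours, so the fast becomes at least 8+2 = 10 h in insulin-treated patients, and glucose would need checking.
- The visit would be longer and tied to a dose time.
- Later cycles would still have no on-drug ECG, so the longer exposure in this trial would not be addressed.

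A Day 1 ECG after the supervised first dose would leave visit 2b alone, but would see only 1−0.5^(12/19) = 35% to 1−0.5^(12/11) = 53% of steady-state exposure. Leaving the schedule as it is would also be defensible.

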4.3. ASSIGNMENT OF PATIENT NUMBER

At the screening visit, each patient will be assigned a unique sequential Screening number. If the patient is randomized, the Randomization number will be assigned in a sequential manner as patients are found to be eligible and are randomized. This number will be used for identification throughout the study and will not be used for any other participant.

If a patient is dropped from the study for any reason, the patient's randomization number will not be reassigned.

5. STUDY MEDICATION

5.1. PRESENTATION, PACKAGING AND LABELING, SUPPLY, AND STORAGE OF THE INVESTIGATIONAL MEDICINAL PRODUCT

5.1.1. Presentation of the Investigational Medicinal Product

In this study the Investigational Medicinal Product (IMP) will be either ladarixin OR matched placebo.

It will be provided in the form of hard gelatin capsules for oral administration, with the following composition:

CCI

Batch release certificate will be provided together with the IMP.

5.1.2. Manufacturing, Packaging and Labelling of IMP

Capsules will be manufactured alternatively by PPD

The primary packaging, labelling and kitting of capsules in blisters to obtain the Patient Kit will be done alternatively by PPD

The study medication will be provided as 7 Patient Kits, each containing 56 capsules covering the treatment period of 14 days.

All labels will be prepared to meet local regulatory requirements. Details of packaging and labelling are reported in Section 14.1.

5.1.3. Supply, Storage and Handling of IMP

An appropriate number of packages will be initially sent to the site as soon as all essential documents and regulatory/ethics approvals have been obtained. IMP re-supply will be planned on demand, according to enrolment rate.

The IMP must be kept at a temperature not exceeding 30°C and must not be frozen.

A temperature monitor will accompany the drug on shipment. Temperature range reached during shipment will be verified on receipt at site, so that potential stability concerns during shipment can be investigated and appropriate action taken.

Once received at the site, the Pharmacist (or designee) will check the package for accurate delivery and acknowledge receipt; any deviations from expected package content (inconsistency, damages) should be immediately reported to Dompé (or appointed CRO) and the use of the drug suspended until authorization for its continued use has been given by Dompé (or appointed CRO).

The IMP must be stored at site in a secure location, in a temperature-controlled room. Temperature records must be available for the CRA to review at monitoring visits; any deviations from the recommended storage conditions should be immediately reported to Dompé (or appointed CRO) and the use of the drug suspended until authorization for its continued use has been given by Dompé (or appointed CRO).

5.1.4. Blinding and unblinding

Appearance, including packaging and labelling, of the IMP (capsules, packaging) will not allow to recognize actual treatment (either ladarixin or placebo).

During the trial, blinding will be broken by the Investigator for emergency purposes only, where knowledge of the blinded treatment could influence further patient care. In addition, safety reports will be unblinded, as per regulatory requirements. Any emergency unblinding must be notified to the CRO's medical monitor.

The sponsor's personnel from the Pharmacovigilance Department of Dompé may break the treatment code for subjects who experience a Suspected Unexpected Serious Adverse Reaction (SUSAR), in order to determine if the individual case requires expedited regulatory reporting.

With the exception of the above-mentioned episodes, the identity of the treatments will remain unknown to the subject, Investigator, site staff, CRO and Dompé's personnel until the study completion and formal unmasking

Study blind will be broken after database lock.

5.2. DOSE, ROUTE AND SCHEDULE OF IMP ADMINISTRATION

Ladarixin will be administered orally at the dose of 400 mg b.i.d. for 7 cycles of 14 days with an interval of 14 days off, for a total duration of 26 weeks. The two daily doses will be administered at about a 12-hour interval (morning and evening; ideally between 6:30/11:30 and 18:30/23:30). At each administration, 2 capsules will be swallowed with a glass of water, at least 2 hours apart from breakfast or dinner. Placebo will be administered with the same treatment schedule.

